#### 12.0 Biostatics and Subsidies

A statistical analysis using IBM SPSS Statistics (Version 28) predictive analytics software will be completed. The STAIC S-Anxiety scale mean score during the treatment period will be compared to the control period mean score using paired-samples t-tests (Spielberger,

1973). The control period mean score will be compared to the baseline. Similarly, the raw score from the FNSC during the treatment period and the raw control period score will be compared using paired-samples t-tests to understand if the children demonstrated a statistically significant change in food neophobia (Pliner, 1994). The control period raw score will be compared to baseline raw score using paired-samples t-tests. Nonparametric analysis will be used as necessary.

The average number of foods tried during the control period will be compared to baseline and the average number of new foods tried during the control period will be compared to the average number of new foods tried in the treatment period to understand if more foods were tried when using the weighted blanket. A paired-sample t-test will be completed to compare the control period to the treatment period. Nonparametric analysis will be used as necessary.

A weighted blanket will be provided to each of the participants of this study for their use following the study at no cost to the participant. The weighted blankets will be purchased by the principal investigator. This study is not funded by grants or subsidies.

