### 4.0 Enrollment/Consenting Process

Children receiving occupational therapy services at Capital Area Speech and

Occupational Therapy to address feeding who have anxiety related to food will be offered enrollment via flyers and word of mouth. The first level of recruitment will include potential participants that have a patient relationship with the principal investigator or are receiving occupational therapy services from another occupational therapist at Capital Area Speech and Occupational Therapy. If 12 participants meeting the inclusion criteria cannot be recruited from Capital Area Speech and Occupational Therapy, the second level of recruitment will occur including other clinics in the Austin, Texas area who have given permission for flyers to be left in their waiting rooms. During the second level of recruitment, potential participants will contact the principal investigator for additional information regarding the study. A flyer will be available to potential participants with information about the study and principal investigator's contact information so that caregivers can ask questions. Potential study participants will only be provided additional information upon request regarding the study.

Recruitment will take place for 2 months and is anticipated to start April 2024 following IRB approval with researchers determining eligibility for the study based on inclusion and exclusion criteria. Participants and at least one guardian of each participant will be required to sign a consent form to affirm that they understand the purpose of this study, risks, and

requirements. To respect potential participant privacy, no information will be collected for research purposes prior to consent form completion. Also, no information of participants who withdraw from this study will be used. To consent to this study, potential participants will be provided with a consent form to review via email prior to signing it. Potential participants will be given an opportunity to speak with the investigator prior to signing the consent form.

No randomization will take place. There will be a control period consisting of usual care occupational therapy lasting 1 month prior to the treatment period lasting 1 month.

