#### 5.0 Study Procedures

- 1. Recruitment
- 2. Consent
- 3. Enrollment of participants based on inclusion and exclusion criteria.
- 4. Guardians of enrolled participants will complete the baseline outcome measure

  Food Neophobia Scale for Children (FNSC) questionnaire consisting of 10 questions

  (Pliner, 1994). Guardians of participants will also complete an initial food list on the
  initial food log form including all foods that the participant currently tolerates. Included
  on the initial food log form will be a place for the caregiver to record the age and weight
  of the child. The weight of the child will be used to calculate the appropriate weight of
  the weighted blanket. The weighted blanket will not exceed 10% of the child's body
  weight. Weighted blankets are commercially available through the company yescool for
  children in weights of ten pounds, seven pounds, five pounds, and three pounds. Each
  participant will receive a weighted blanket that is approximately 10% of their body

weight but does not exceed 10% of their body weight. For example, if a child weighs 55 pounds, they will receive a five-pound weighted blanket. The initial food log form including the initial food list and weight of the child will be scanned and returned to the caregiver prior to the control period. The FNSC will be collected.

- 5. Participants will receive occupational therapy services treatment as usual without use of a weighted blanket for 1 month. During this period, participants will complete the S-Anxiety scale of the State-Trait Anxiety Inventory for Children (STAIC) three times per week upon sitting at the table prior to a meal (Spielberger, 1973). The S-Anxiety scale questionnaire will take about 8-12 minutes for a child to complete the first time and 5-8 minutes for repeated administrations. All forms and scales necessary for the control period will be provided to the caregivers prior to the control period of the study.
- 6. After the 1-month control period, caregivers will complete the FNSC and complete the second food list adding any new foods to the initial food log (Pliner, 1994). The principal investigator will collect the FNSC and the initial food log form at this time.

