- 7. Following the 1-month control period, participants and their guardians will receive a weighted blanket with verbal and written instructions for use and safety. The participants will continue usual care occupational therapy treatment during the treatment period. The caregivers will be provided with copies of the S-Anxiety scale of the STAIC, new food log, and a copy of the initial food log for reference (Spielberger, 1973). Participants will be instructed to use the weighted blanket for at least 5 minutes and no more than 15 minutes while participating in a quiet enjoyable activity prior to a meal with guardian supervision. Guardians will be responsible to keep the weighted blanket when not in use. Due to busy family schedules, it may not be possible to use

the blanket daily, therefore, the family will be asked to offer use of the blanket a minimum of 3 meals a week. On the days that the weighted blanket was used, the participant will complete the S-Anxiety scale of the STAIC at the table where they will consume the meal, following using the blanket and before eating the food (Spielberger, 1973). The guardians will be asked to record any new foods tried during the meal on the new food log along with the date each time the participant uses the weighted blanket.

- Upon completion of the 1-month treatment period, the guardians will complete the FNSC (Pliner, 1994). The principal investigator will collect the FNSC, new food log, and S-Anxiety scale of the STAIC at this time either through HIPAA protected email or in-person (Spielberger, 1973).
- 10. Once the study is completed the guardians will be gifted the weighted blanket to use as they deem appropriate

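### The planned comparison of control-month S-Anxiety with baseline cannot be run, because no S-Anxiety score is scheduled before the control month

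*Combined protocol and SAP*

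**What the plan says.** Section 12.0 first compares mean S-Anxiety in the treatment month with the mean in the control month by paired t-test. It then adds: "The control period mean score will be compared to the baseline". The FNSC is taken up next, with its own sentence: "The control period raw score will be compared to baseline raw score using paired-samples t-tests". Foods tried have a separate paragraph.

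Section 5.0 sets out the collection. In step 4, before the control month, "Guardians of enrolled participants will complete the baseline outcome measure", which is the FNSC. The same step adds the food list ("Guardians of participants will also complete an initial food list on the" initial food log form) and the child's age and weight. S-Anxiety first appears in step 5, within the control month, to be completed "three times per week upon sitting at the table prior to a meal". In the treatment month (step 7) it is completed on days when the blanket was used.

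On design, Section 4.0 states: "No randomization will take place". One month of usual care is followed by one month with the blanket.

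**The concern.** The analysis section calls for a score that the procedures never collect. The FNSC and the food list both have a value from before the control month; S-Anxiety does not.

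Every child has the control month first, so any change in repeated self-reported anxiety over time (getting used to the form, regression to the mean) falls in the treatment-versus-control contrast along with any effect of the blanket. Control versus baseline is the only planned view of S-Anxiety change while no blanket is in use. The plan gives no purpose for this comparison, so that use of it is the review's reading.

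If the gap is noticed only at analysis, the easy repair is to call the first control-month form the baseline. That choice would be made after data collection, and the form would be compared with a mean that includes it.

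**Working it through.** **1. Which measure the sentence concerns.** It follows directly on the S-Anxiety comparison and keeps that comparison's term, mean score. The FNSC is called a raw score and has its own baseline sentence. The disputed sentence is therefore about S-Anxiety.

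**2. Scheduled S-Anxiety scores per child.**

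| Time | Source | Scores |
|---|---|---|
| Before control month | Section 5.0 step 4 | 0 |
| Control month | Section 5.0 step 5, 3 per week | 3 × 4 = 12, up to about 13 |
| Treatment month | Section 5.0 step 7, at least 3 meals a week offered | about 12 or more if the blanket is used at that rate |

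Nothing else supplies a baseline. The section on sources of research material lists no earlier STAIC and rules out record review, and Section 4.0 bars research data collection before consent. Step 5 has forms handed out before the control month, but for use during it.

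**3. Using the first control form as baseline.** With k forms in the control mean,

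mean − first = ((k − 1)/k) × (mean of the others − first).

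The factor is 11/12 = 0.917 at k = 12 and 12/13 = 0.923 at k = 13, so the estimated change shrinks by about 8%.

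**4. Precision of possible replacements.** The documents give no SD, so results are in units of σ, the within-child SD of one form. Assumptions: 12 forms per month, independent errors, and no between-child variation in the true change. Section 2.0 gives a minimum of 7 children and a target of 12.

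95% CI half-width = t(0.975, n − 1) × SD / √n, with t = 2.447 (n = 7) and 2.201 (n = 12).

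| Contrast | SD of a child's difference (σ) | n = 7 | n = 12 |
|---|---|---|---|
| One pre-control form vs control mean | √(1 + 1/12) = 1.041 | 0.963 | 0.661 |
| Three pre-control forms vs control mean | √(1/3 + 1/12) = 0.645 | 0.597 | 0.410 |
| Last vs first control week (3 forms each) | √(1/3 + 1/3) = 0.816 | 0.755 | 0.519 |
| Treatment vs control (12 vs 12) | √(1/12 + 1/12) = 0.408 | 0.378 | 0.259 |

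**5. Sensitivity to independence.** With AR(1) correlation 0.5 between successive forms, the half-widths at 7 / 12 children become 0.794 / 0.545 (three pre-control forms), 1.020 / 0.701 (last vs first week) and 0.597 / 0.410 (main contrast). Both replacement checks stay less precise than the main contrast. For three pre-control forms, the ratio to the main contrast falls from 0.597/0.378 = 1.58 to 0.794/0.597 = 1.33. Differences between children in drift would widen the checks; differences in response to the blanket would widen the main contrast.

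**The case against.** The mismatch itself is hard to dispute; the case on the other side concerns its weight and the remedy.

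- **It is one supporting sentence in a small pilot.** The main comparison can be computed without it, and deleting it would remove the inconsistency. That is true, but deletion would also remove the only planned look at S-Anxiety change without the blanket.
- **Using the first form as baseline does little numerical harm.** If every child has the same number of forms, the factor in step 3 is constant, so the paired t statistic and p-value match those with the form left out of the mean; only the estimate shrinks, by about 8%. This stands. The firmer objections are that the choice would be made late and that a single form is imprecise.
- **Extra forms are a burden.** Three child-completed forms are more than the single guardian-completed FNSC and food list. They add a week, in the same usual-care condition as the control month. Section 11.0 lists time commitment as a reason for withdrawal, and Section 4.0 discards withdrawn children's data. This stands, and it favours the option without added forms.
- **The test can be inferred.** Paired t-tests are named on either side of the sentence. The missing test name is minor.
- **Some material is not shown.** The contents list a study schema that could not be seen, and the S-Anxiety form itself may carry a date field. If the schema does show an earlier S-Anxiety score, Section 5.0 would still need to be brought into line with it.

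**Conclusion.** The concern holds. Section 12.0 specifies an S-Anxiety comparison with baseline for which Section 5.0 schedules no baseline scores, so it cannot be run as written. This rests on the procedural text alone and needs no numerical assumption. The gap is specific to S-Anxiety and leaves the treatment-versus-control comparison intact, so it should be corrected but does not undermine the main analysis.

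The half-widths depend on the assumed 12 forms per month and the stated error models. Under both models, the three-form check and the week-to-week check are less precise than the main contrast. Neither can show that drift is absent with 7 to 12 children.

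**What to change.** Choose one option before enrolment.

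**(a) Collect a baseline.** Add to step 4 three pre-meal S-Anxiety forms, completed after consent in the week before the control month. In Section 12.0, state that each child's control-month mean will be compared with the mean of the pre-control forms by paired-samples t-test, with a 95% CI. By the protocol's own timings this costs 8 + 5 + 5 = 18 to 12 + 8 + 8 = 28 minutes per child, plus the extra week.

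**(b) Add no forms.** Replace the sentence with a prespecified paired comparison of each child's mean S-Anxiety in the last and first weeks of the control month, with a 95% CI. Describe it as change within the month, not change from baseline. The cost is analysis wording and a date on each form.

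Ask for a date on every S-Anxiety form so that forms can be put in order. Step 7 asks for new foods to be recorded "on the new food log along with the date each time the participant uses the weighted blanket", but the text asks for no date on the S-Anxiety forms.

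Under either option, state that the check is imprecise at 7 to 12 children and that a null result does not rule out drift. Do not use the first control-month form as baseline while it also counts in the control mean.

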#### **Proposed Pilot Study**

This small experimental pilot study addresses the knowledge gap related to the use of weighted blankets for children with anxiety related to food and eating. My plan includes recruiting a minimum of seven children who receive OT treatment at the clinic where I work and clinics in the surrounding area. However, I would like permission to recruit twelve children due to concerns with attrition. The design of the study will include a control period prior to the treatment period. This study will seek to understand if children improve their ability to self regulate and calm with the use of a weighted blanket when trying new foods. It will also attempt to research whether children improve novel food consumption using a weighted blanket.

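### Section 12.0 tests the two monthly FNSC changes separately and plans no estimate, with an interval, of the difference between them; the STAIC comparison has the same exposure to a time trend.

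*Combined protocol and SAP*

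**What the plan says.** Under Proposed Pilot Study (Section 2.0), "The design of the study will include a control period prior to the treatment period", and one aim is to learn "if children improve their ability to self regulate and calm with the use of a weighted blanket when trying new foods". Section 4.0 rules out randomisation and sets one month of usual-care occupational therapy before one month of treatment. Section 5.0, step 7, continues that therapy during the blanket month.

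Section 5.0 has guardians complete the FNSC three times: at baseline (T0), after the control month (T1) and after the treatment month (T2). The child completes the STAIC S-Anxiety scale repeatedly within each month. No STAIC is scheduled before the control month begins.

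Section 12.0 plans two separate FNSC tests:

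- T2 vs T1: "the raw score from the FNSC during the treatment period and the raw control period score will be compared using paired-samples t-tests", with the purpose "to understand if the children demonstrated a statistically significant change in food neophobia".
- T1 vs T0: "The control period raw score will be compared to baseline raw score using paired-samples t-tests".

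For anxiety, "The STAIC S-Anxiety scale mean score during the treatment period will be compared to the control period mean score using paired-samples t-tests". Section 12.0 allows nonparametric analysis where needed. That changes the test, not the quantity being tested.

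**The concern.** Every child has the control month first, and therapy for feeding problems runs through both months. The FNSC change from T1 to T2 therefore contains a further month of therapy and elapsed time as well as any blanket effect. What the blanket adds is the treatment-month change minus the control-month change, and Section 12.0 plans neither a test nor an interval for that difference.

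Placing the two tests side by side does not supply it. One significant and one non-significant result do not show that the two changes differ. With 7 to 12 children, the control-month test will often miss an improvement that is really there.

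The STAIC treatment-versus-control difference bears on the calming aim and is open to the same trend. At stake is whether the report can separate the blanket from continuing therapy, or might be read as doing so when it cannot.

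**Working it through.** **Inputs from the documents.** n = 7 (recruitment minimum) and n = 12 (number for which permission is sought); three FNSC times; fixed order; therapy ongoing. The documents state no alpha, SD, expected change or power, so there is no planned figure to reproduce.

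**Assumptions for illustration.** Two-sided 5% level; normal, independent errors at each visit with variance 0.5, so that a monthly change has SD 1; no blanket effect; drift in the direction of improvement, in SD of a monthly change.

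**1. T2 vs T1 under equal drift d.** The paired t statistic is noncentral t with n − 1 degrees of freedom and noncentrality d√n. For d = 0.5:

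- n = 12: noncentrality 0.5 × 3.464 = 1.73, critical value 2.201, rejection 35.3%.
- n = 7: noncentrality 0.5 × 2.646 = 1.32, critical value 2.447, rejection 20.1%.

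| Equal drift (SD) | n = 12 | n = 7 |
|---|---|---|
| 0 | 5.0% | 5.0% |
| 0.3 | 15.8% | 10.3% |
| 0.5 | 35.3% | 20.1% |
| 0.8 | 71.4% | 42.8% |

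**2. Does T1 vs T0 give warning?** Simulation of T0, T1 and T2, 200,000 replicates, d = 0.5 in both months:

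| Pattern | n = 12 | n = 7 |
|---|---|---|
| Both tests significant for improvement | 7.3% | 1.9% |
| Second significant, first not | 28% | 18% |

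Among trials with a significant T2 vs T1, the control-month test also flags improvement in about 7.3/35.3 = 21% (n = 12) and 1.9/20.1 = 9% (n = 7). The joint rate is low partly because T1 enters both changes with opposite sign.

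**3. The missing contrast.** For each child, D = (T2 − T1) − (T1 − T0) = T2 − 2·T1 + T0. Equal drift cancels, and the simulated rejection rate is 5% at both sample sizes.

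**4. Its precision.** With visit-error variance σ², Var(D) = (1 + 4 + 1)σ² = 6σ², against 2σ² for one change. The SD ratio is √3 = 1.73. The 95% CI half-width is t(0.975, n − 1) × SD/√n, taken at the true SD:

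| | Single change | Contrast D |
|---|---|---|
| n = 12 | 2.201/3.464 = 0.64 | 0.635 × 1.732 = 1.10 |
| n = 7 | 2.447/2.646 = 0.92 | 0.925 × 1.732 = 1.60 |

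**5. Unequal drift.** If all improvement falls in the control month (0.8 SD, then 0), T2 vs T1 stays at 5%. D then rejects in 31% (n = 12) and 18% (n = 7), almost always against the blanket.

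**6. STAIC.** Assume 12 evenly spaced scores a month. The period means are then centred at 0.5 and 1.5 months, so a linear drift of b per month shifts their difference by (1.5 − 0.5)b = b. The table in step 1 applies if drift is expressed in SD of that difference. With no score before the control month, there is no control-month change to subtract, so D has no STAIC counterpart.

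**The case against.** **The control month is already analysed.** This stands in part. A reader might infer that the control month is not used as a control for FNSC. That goes too far, because T1 vs T0 is tested and the two planned mean changes could be subtracted by hand. What is missing is the planned comparison and its interval.

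**Rejection under drift is not an error of the test as written.** This stands. A reader might infer that the T2 vs T1 test has a false-positive rate of 20% to 35%. The documents do not support that. Section 12.0 frames the FNSC question neutrally as whether neophobia changed; if it drifted, rejecting no change is correct. The documents do not say that the change will be credited to the blanket, although the study aim makes such a reading easy. With no drift the planned tests hold 5%.

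**The contrast trades one assumption for another and is imprecise.** Both parts stand. The documents do not show which shape of drift is likelier, and under front-loaded improvement the planned test does better. Power for a true added effect of 0.8 SD is only 31% at n=12 and 18% at n=7. This is why the contrast belongs beside the planned tests as an exploratory estimate, not in their place.

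**STAIC gets no analytic remedy.** True of the fix below. The repeated scores might support a model with a time slope and a step at the start of treatment, but that is a larger change and is not asked for here.

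**The new-foods comparison might seem to handle drift already.** A reader might infer this, but the recording rules differ. Step 6 of Section 5.0 updates the list for the whole control month, whereas step 7 logs foods at blanket meals. Nothing here rests on that outcome.

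**Conclusion.** The omission is a matter of text and rests on no assumption: Section 12.0 plans no estimate with an interval of the difference between the two monthly FNSC changes. Its consequence is conditional. At an assumed equal drift of 0.5 SD, with no blanket effect and independent visit errors, T2 vs T1 is significant in 35% (n=12) or 20% (n=7) of trials, and the pattern of second significant, first not, arises in 28% or 18%. These count as errors only if the result is attributed to the blanket. The STAIC difference has the same exposure to a time trend and cannot be given the same contrast. For an unrandomised pilot of this size, this is a cheap improvement of low severity, not a demonstrated error rate.

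**What to change.** In Section 12.0:

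1. Add each child's FNSC contrast (T2 − T1) − (T1 − T0). Report its mean with a 95% CI as an exploratory pilot estimate of the added effect, beside the two planned tests.
2. State that neither the FNSC change from T1 to T2 nor the STAIC treatment-versus-control difference will on its own be attributed to the blanket.
3. State that the contrast removes only equal month-to-month drift, and that front-loaded improvement, regression to the mean or expectation effects can bias it, including against the blanket.

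The cost is one derived variable and a few sentences. No new data or visits are needed, since all three FNSC scores are already collected. The downside is width: about 1.73 times that of a single change under independent errors, so the interval will be wide at either sample size. The change does not remove the STAIC time trend; it only limits what is claimed from that comparison.

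### The control-versus-baseline food comparison either cannot go below zero or compares unlike counts, so it does not measure change in food variety

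*Combined protocol and SAP*

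**What the plan says.** All references are to the combined protocol and SAP.

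- **Baseline (section 5.0, step 4).** Guardians fill in an "initial food log form including all foods that the participant currently tolerates". The form is scanned and handed back before the control month.
- **End of the control month (section 5.0, step 6).** Caregivers "complete the second food list adding any new foods to the initial food log". Then: "The principal investigator will collect the FNSC and the initial food log form at this time".
- **Treatment month (section 5.0, step 7).** On a separate form, guardians "record any new foods tried during the meal on the new food log along with the date".
- **Analysis (section 12.0).** "The average number of foods tried during the control period will be compared to baseline". The same sentence goes on to compare new foods between the control and treatment periods. The only test named for food counts is for that second contrast: "A paired-sample t-test will be completed to compare the control period to the treatment period". The paragraph ends: "Nonparametric analysis will be used as necessary".
- **Size (section 2.0, Proposed Pilot Study).** "My plan includes recruiting a minimum of seven children"; permission is sought for twelve.

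No step asks caregivers to remove a food from the list, to rebuild it from scratch, or to count new foods tried in any period before the control month.

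**The concern.** There is no randomization, so the control month is the study's only comparator. Its comparison with baseline is the plan's check on what usual-care occupational therapy does to the number of foods before the blanket is introduced. That check is informative only if the two counts are of the same thing and the difference can move in either direction. Here the second count is built by extending the first, and losses are not recorded. A child who adds one food and drops three would be scored as a gain of one. A report that usual care widened the diet could then reflect how the form is filled in. The analyst cannot repair this afterwards, because dropped foods will not have been written down.

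**Working it through.** The plan gives no power calculation, alpha, effect size or standard deviation, so there is no figure of its own to reproduce. The check is logical first, then illustrative.

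**Notation.** For child i, B is the number of foods on the initial list, A the number added during the control month, and L the number no longer accepted by the end of it. B and A are recorded; L is not.

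**Reading 1: the control figure is the extended list.**
- Recorded change = (B + A) − B = A, which is zero or more for every child.
- True net change = A − L.
- Recorded minus true = L. The overstatement equals the number of foods dropped, and is nil only when none are.
- Example: A = 1 and L = 3 gives a recorded change of +1 and a true net change of −2.

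**Reading 2: the control figure is the month's new foods only.**
- Recorded change = A − B: foods tried in one month minus all foods tolerated at entry.
- With an assumed 15 foods on the list and 2 new ones, this is 2 − 15 = −13. With 2 new foods and assumed lists of 5 to 30, it runs from −3 to −28. The value mostly reflects the length of the initial list.

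Section 12.0 speaks of foods for the baseline contrast and of new foods for the treatment contrast. That leans towards reading 1 but does not settle it.

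**How often reading 1 would look like an increase when nothing changed.** Assumptions, none from the documents: additions per child are Poisson with mean λ; unrecorded losses are Poisson with the same mean, so the true net change is zero; a paired t-test is used at two-sided alpha 0.05; 20,000 simulated replicates.

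| λ | n = 7: increase declared | n = 12: increase declared |
|---|---|---|
| 0.1 | 0.2% | 2% |
| 0.25 | 5% | 20% |
| 0.5 | 25% | 62% |
| 1 | 67% | 96% |
| 2 | 95% | about 100% |
| 3 | 99% | 100% |

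When losses are counted as well, the same test rejects in 0.1% to 5.4% of replicates at n = 7 and 1.4% to 5.0% at n = 12. The mean change is then negative in about 31% to 48% of replicates. Under add-only recording it is never negative.

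**An increase is not guaranteed.** The probability that no child adds a food is exp(−nλ). At n = 7 it is exp(−0.7) = 0.50 for λ = 0.1, exp(−1.75) = 0.17 for λ = 0.25 and exp(−3.5) = 0.03 for λ = 0.5.

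**Exact sign test, if one were used.** When k children add a food and none can show a loss, two-sided p = 2 × 0.5^k. For k = 5, p = 0.0625; for k = 6, 0.031; for k = 7, 0.016.

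**The case against.** The strongest reply has four parts.

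1. *The aim concerns novel food consumption, and dropping a food does not undo having tried a new one.* This stands in part. Under reading 1 the difference is a real quantity, the number of foods added in the month. But it is then a count for one month and not a change from baseline, and it says nothing about whether the range of accepted foods grew.

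2. *No test is assigned to this contrast, so the p-values are hypothetical.* This stands. Section 12.0 names a paired t-test for the neophobia scale's baseline contrast, but for food counts only for control versus treatment. The rejection rates above show how far the result could mislead under assumed rates; they do not predict what this study will report.

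3. *The blanket is not judged on this contrast.* This stands. A reader might infer that the defect carries over to the blanket result. The documents do not support that: control versus treatment sets additions against additions and does not use the baseline list. (The two logs are kept differently, once at month end and at each blanket meal, but that is a separate matter.)

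4. *The neophobia scale, completed at baseline and again after the control month, already gives a usual-care check that can move either way.* True for neophobia. It does not repair the food count.

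**Conclusion.** The point holds. As written, the contrast is either one-directional or a comparison of unlike quantities, and section 12.0 does not say which. Under the extended-list reading it cannot detect a decline, and it is biased upward as a measure of change in food variety by the number of foods dropped. Under the new-foods-only reading it is not interpretable.

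A reader might infer that the plan is bound to show usual care increasing foods. The documents do not support that. The add-only list guarantees a change of zero or more, and only under one of the two readings; an increase needs at least one child to add a food, and at low addition rates none may. The chance of a spurious significant increase at seven children runs from about 0.2% to 99% across the assumed rates, so no single figure should be quoted. The conclusion about direction rests only on how the form is built and needs none of these assumptions. Its scope is limited to a pre-blanket comparison in a pilot of seven to twelve children.

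**What to change.** **Preferred.** Delete the control-versus-baseline food comparison from section 12.0. Report the control-month additions descriptively, as new foods per child per month, and draw no inference from them that usual care widened the diet. This costs one sentence and loses no usable information.

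**If a change from baseline is wanted.** Have caregivers also mark, on the existing food log at the end of the control month, the foods on the list that the child no longer accepts. Define the outcome in section 12.0 as additions minus foods marked, which can go either way, and name its analysis. The form is already collected at that visit, so the cost is slightly more caregiver recording. The instruction must be in place before the first family finishes the control month.

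**Optional.** A line on the initial log asking how many new foods the child tried in the month before enrolment would give a like-for-like reference for the control-month count. It would rest on recall and be rough, so it should be used descriptively at most.
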